5.5 Safety Analyses

Unless stated otherwise, all safety analyses will be performed on the SS.

5.5.1 Extent of Exposure

Administration of treatments will be listed by sequence. Exposure data will be listed only.

5.5.2 Adverse Events

An Adverse Event is any untoward medical occurrence in a participant or clinical study participant, temporally associated with the use of study medication, whether considered related to the study medication.

Adverse events with start date/time prior to first treatment are defined as pre-treatment. These events will not be included in any tabulated summaries but will be listed.

Treatment emergent AEs (TEAE) are all AEs starting on or after the date/time of first treatment and up to including 4 days after last treatment, or any unresolved event already present before administration of treatment that worsens in intensity following exposure to the treatment.

AEs with a start date after 4 days of last treatment are defined as post-treatment. These events will not be included in any tabulated summaries but will be listed.

In case of missing or partially missing AE dates, the following rules will apply. Start and stop dates of AEs will be displayed as reported in the participant data listings (ie, no imputed values will be displayed in data listings).

The following rules will be applied for partial start dates and time:

- If only the month and year are specified and the month and year of the first treatment is not the same as the month and year of the start date, then use the 1st of the month, or the date of Screening if this is later (if the imputation results in an end date that is earlier than the start date, then use the 1st of the month). If time is missing, it will be imputed as 00:00 h
- If only the month and year are specified and the month and year of the first treatment is the same as the month and year of the start date, then use the date of the first treatment. If the imputed start date that is after the specified end date, then use the 1st of the month, or the date of Screening if this is later (if the imputation results in an end date that is earlier than the start date, then use the 1st of the month). If the imputed date is the date of treatment then time will be imputed as the start time of the treatment (ie, event will be regarded as treatment emergent)
- If only the year is specified, and the year of the first treatment is not the same as the year of the start date, then January 01 will be used. If time is missing, it will be imputed as 00:00 h
- If only the year is specified, and the year of the first treatment is the same as the year of the start date, then the date of the first treatment will be used. If this results in an imputed start date that is after the specified end date, then January 01, or the date of Screening if this is later will be used (if the imputation results in an end date that is earlier than the start date, then January 01 will be used). If the imputed date is the date of first treatment then time will be imputed as the start time of the treatment (ie, event will be regarded as treatment emergent)
- If the start date is completely unknown, then use the date of first treatment. If this results in an imputed start date that is after the specified end date, then use January 01 of the year of the end date, or the date of Screening if this is later.

The following rules will be applied for partial stop dates:

- If only the month and year are specified, then use the last day of the month

- If only the year is specified, then use December 31 of the known year
- If the stop date is completely unknown, do not impute the stop date

Missing or partially missing date and/or times will be imputed as described in [Table 9](#) for the calculation of duration of each AE. AE duration is computed and reported in day and time format.

Table 9 Calculation Rules for Duration of AEs

Data Availability	Onset Date/Time	Outcome Date/Time	Calculation Rules
Complete data	D1/T1	D2/T2	Duration = $(D2-D1)*24+(T2-T1)$
End time missing	D1/T1	D2/--	End time is substituted by time 23:59h (=23.98 in decimal format). Duration= $(D2-D1)*24+(23.98-T1)$
Start time missing	D1/--	D2/T2	Onset time is substituted by 00:00h. Duration= $(D2-D1)*24+T2$
Start and end time missing	D1/--	D2/--	Duration= $(D2-D1)*24$
Start day and time missing	--/--	D2/T2	Duration= $(D2-D0)*24+(T2-T0)$ For a participant in the SS, D0 and T0 are the date and time of the first administration of study medication and for screen failures, D0 is the date of the Screening Visit date and T0=00:00h.
End day and time missing	D1/T1	--/--	If the stop date is missing, duration will not be calculated.
Start and end date missing	--/--	--/--	If the stop date is missing, duration will not be calculated.

The duration of each AE will be calculated as follows and will be presented in dd:hh:mm format where dd represent days, hh: hours, and mm: minutes:

$$\text{Duration of AE} = \text{End date/time of AE} - \text{Start date/time of AE} \quad (2)$$

Adverse events will be assigned to Treatment Periods, based on the onset date/time of the AE. Assignment to Treatment Periods will be done after missing dates have been imputed as described above. AE will be assigned to a treatment based on the treatment received in the Treatment Periods as given in [Table 10](#).

Table 10 AE Treatment Period Assignment

Study	Period	Start	End
UP0152	Treatment Period 1	Start date is on or after administration of treatment in Treatment Period 1	Prior to administration of treatment in Treatment Period 2
	Treatment Period 2	Start date is on or after administration of treatment in Treatment Period 2	Prior to administration of treatment in Treatment Period 3
	Treatment Period 3	Start date is on or after administration of treatment in Treatment Period 3	

The following summaries will be provided by formulation and feeding condition groups:

- Incidence of TEAEs – Overview
- Incidence of TEAEs
- Incidence of Serious TEAEs
- Incidence of TEAEs leading to study discontinuation
- Incidence of TEAEs leading to permanent treatment discontinuation
- Incidence of TEAEs by maximum intensity
- Incidence of TEAEs by relationship to study medication

AEs will be presented as “number of participant (percentage of participant) [number of events]”. In this style of output, “[number of events]” will include all cases of an AE including repeat occurrences in individual participant, while “number of participant” will count each participant only once.

AEs will be presented by system organ class (SOC), high level term (HLT) and preferred term (PT) in a frequency table, giving the number of events, the number of participants, and the percentage of participants who experienced the event. Participants with multiple AEs are only counted once within each PT, each HLT and within each SOC.

Summaries by maximum severity will count each participant at most once within each MedDRA level based on the maximum severity/event intensity within that MedDRA level.

In summaries including intensity, the following intensity categories will be summarized: ‘Mild’, ‘Moderate’, ‘Severe’. Participants who experience the same event multiple times will be included in the most severe category for tabulations by maximum intensity. Events with missing intensity will be considered as ‘Severe’ events for summary purposes but recorded as missing in the listings.

All summaries will be sorted alphabetically by SOC. Within SOC, it will be sorted by decreasing frequency of PT.

A by-participant listing will be presented for by formulation and feeding condition for all AEs for the SS. This will include reported term, SOC, PT, the onset date/time and outcome date/time

of the event (including relative days), stop date and time (or ongoing, if applicable; relative days), the AE duration, severity, relationship, action taken, and outcome. In addition, the listing will flag TEAEs, Serious TEAEs, and AE of special interest. A glossary of AE terms including reported term, SOC and PT will also be presented.

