8.4.1 Time period and frequency for collecting AE and SAE information

All AEs and SAEs will be collected from the signing of the ICF until the SFU or ETV (if applicable) at the time points specified in the Schedule of Activities (Section 1.3) and must be reported in the ClinBase even if no study intervention was taken but specific study procedures were conducted. This includes all AEs not present before the initial visit and all AEs that recurred or worsened after the initial visit.

All SAEs will be recorded and reported to the UCB Study Physician or designee immediately and under no circumstance should this exceed 24 hours, as indicated in Appendix 3 (Section 10.3). The investigator will submit any updated SAE data to the sponsor within 24 hours of it being available.

Investigators are not obligated to actively seek information on AEs or SAEs after conclusion of the study participation. However, if the investigator learns of any SAE, including a death, at any time after a participant has been discharged from the study, and the investigator considers the event to be reasonably related to the study intervention or study participation, the investigator must promptly notify the sponsor.

The method of recording, evaluating, and assessing causality of AE and SAE and the procedures for completing and transmitting SAE reports are provided in Appendix 3 (Section 10.3).

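### An AE that starts before the first dose and worsens after dosing is both a TEAE and barred from every AE table, and Table 10 gives it no treatment

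*SAP*

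**What the plan says.** Three rules in SAP 5.5.2 apply.

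- **Pre-treatment AEs.** "Adverse events with start date/time prior to first treatment are defined as pre-treatment. These events will not be included in any tabulated summaries"; they are only listed. No exception is made for worsening.
- **TEAEs.** There are two limbs. The onset limb reads "Treatment emergent AEs (TEAE) are all AEs starting on or after the date/time of first treatment and up to including 4 days after last treatment". The worsening limb adds "any unresolved event already present before administration of treatment that worsens in intensity following exposure to the treatment".
- **Assignment to treatment.** "Adverse events will be assigned to Treatment Periods, based on the onset date/time of the AE". The earliest row of Table 10 opens with "Start date is on or after administration of treatment in Treatment Period 1". The TEAE summaries are all by formulation and feeding condition, so a tabulated event needs a treatment.

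Protocol 8.4.1 collects AEs from signature of the consent form and includes "all AEs that recurred or worsened after the initial visit". Protocol 9.2.4 makes the occurrence of TEAEs, of treatment-emergent SAEs and of TEAEs leading to withdrawal the secondary safety endpoints. It separates pre-treatment from treatment-emergent events by IMP intake and has no rule for worsening.

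**The concern.** The pre-treatment rule looks only at the start of the event, while the worsening limb exists to capture events that started earlier. For an AE with onset on Day -1 that becomes more intense after the Day 1 dose, one rule forbids tabulation and the other requires it. A programmer must choose, and the choice changes a secondary endpoint. Choosing the TEAE definition is still not enough, because assignment by onset leaves the event without a column.

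The events concerned are within the planned data: screening lasts up to 28 days, and the Schedule of Activities has AE review at Screening and on Day -1. Hypersensitivity is an AE of special interest, and its listing in SAP 6.1.7 is also by formulation and feeding condition. A rash that was present before dosing and worsened afterwards would have no group there either.

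There is a second, smaller question. Doses are given on Days 1, 6 and 11, with a different treatment each time. An AE that starts mild in Period 1 and becomes severe after the Period 2 dose is assigned by its onset. If it stays on one record, the maximum-intensity table shows it as severe under the Period 1 treatment.

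**Working it through.** The plan gives no figure to reproduce, so the check applies the SAP rules literally. Inputs: doses at 0, 120 and 240 h (Days 1, 6 and 11; SAP 1.2), the onset limb closing 4 days (96 h) after the last dose, and Table 10 assignment by onset.

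| Onset (h) | Worsening (h) | Pre-treatment | TEAE by onset | TEAE by worsening | Period by onset | Period of worsening |
|---|---|---|---|---|---|---|
| -20 | none | yes | no | no | none | – |
| -20 | 2 | **yes** | no | **yes** | **none** | 1 |
| -20 | 122 | **yes** | no | **yes** | **none** | 2 |
| 50 | none | no | yes | no | 1 | – |
| 50 | 122 | no | yes | yes | 1 | 2 |
| 50 | 242 | no | yes | yes | 1 | 3 |
| 130 | 242 | no | yes | yes | 2 | 3 |
| 250 | none | no | yes | no | 3 | – |

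**Step 1: the contradiction.** It occurs only in rows 2 and 3, where onset is before the first dose and worsening follows a dose. Those rows also have no period by onset.

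**Step 2: what the worsening limb adds.** An event can qualify by worsening only if it was present before a dose. If its onset was at or after the first dose, the onset limb already makes it a TEAE. The limb can therefore add only events with onset before the first dose, and these are exactly the events that the pre-treatment rule keeps out of tables. Its net contribution to the tables is zero.

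**Step 3: onset between doses.** Rows 5 to 7 are not pre-treatment and are tabulated. The open point is that the period of onset and the period of worsening differ.

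**Step 4: does the cross-period rule favour a treatment?** Across the six sequences the Period 1 to Period 2 pairs are A→B, B→C, C→A, A→C, B→A and C→B. Every ordered pair occurs once, and the same is true for Period 2 to Period 3. With sequences filled equally, no treatment is favoured by design.

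**Step 5: size.** One omitted participant is 1/18 = 5.6 percentage points. This assumes that all 18 randomized participants are dosed and in the Safety Set, and that the participant has no other TEAE in the same table row under that treatment.

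**The case against.** The strongest reply is that the worsening limb is an implied exception: it would be pointless if the pre-treatment sentence overrode it, so a sensible programmer would tabulate the event. That is a fair guess at intent. But the SAP does not say so, and the guess still leaves no row in Table 10.

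A second reply is that the CRF may handle this. If worsening is entered as a new AE with its own onset, both problems disappear. Protocol 10.3.1 counts an increase in intensity of a pre-existing condition as an AE, which leans that way. However, neither document requires a new record when an AE already recorded worsens. Protocol 10.3.3 has updated information entered in the existing ClinBase record and places each AE in one intensity category, which leans the other way. The CRF is not among the documents, so the point stands on what is written.

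Third, pre-treatment events are still listed, the AE listing flags TEAEs, and with 18 participants each case can be inspected. This limits the harm. It does not make the tables right, and listing and tables could disagree.

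Four stronger readings are tempting, and the documents do not support them:

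- *Any AE present before any of the three doses is barred from tables.* The exclusion refers to the first treatment only.
- *Assignment by onset gives a between-dose event to the wrong treatment.* The event did begin under the earlier treatment, and the worsening limb does not say whether it means the first dose or each dose. This is partly a convention.
- *The safety comparison is biased.* The summaries are descriptive and the sequences are balanced, so no direction is shown.
- *The effect could be 1/12 = 8.3 points.* Twelve is a completer count from the power calculation; safety percentages use the Safety Set.

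**Conclusion.** The point holds for AEs that start before the first dose and worsen after dosing. SAP 5.5.2 defines them as TEAEs, excludes them from every table and gives them no treatment. Applied literally, the rules can undercount the secondary safety endpoint by up to one participant per such event. The conclusion assumes that the worsening stays on the existing AE record, which the documents neither require nor rule out.

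For AEs that start between doses, only the place where the higher intensity is shown is open. This is a lesser matter that the SAP should settle explicitly. No event counts are given. Few such events are likely with three single doses in 18 healthy participants, so the practical effect is probably small. The reason to act is that a secondary endpoint, which also feeds the registry tables in SAP 6.5, should not rest on two definitions that conflict.

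**What to change.** 1. In SAP 5.5.2, limit the pre-treatment category: *Pre-treatment AEs are those that start before the first dose and do not worsen in intensity after it.*
2. Add to Table 10: *An AE that qualifies as a TEAE by worsening is assigned to the treatment most recently received before the worsening, using the date/time and intensity of the worsening.*
3. Instruct the site to enter a post-dose worsening as a new AE record with its own onset, leaving the earlier intensity on the existing record. This step is needed because a date of worsening is not shown to be collected: the AE listing fields in SAP 5.5.2 do not include one. It also settles the between-dose case, since the new record falls into the later period by its own onset.

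The cost is two SAP sentences and one AE completion instruction, with no change to design or sample size. The downside is that one continuing event may appear under two treatments and add to the event counts. A table footnote should say so.

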1 PROTOCOL SUMMARY

1.1 Synopsis

Protocol title: An open-label, randomized study to evaluate the relative bioavailability of a new tablet formulation of minzasolmin and the potential effect of food on the pharmacokinetics of minzasolmin in healthy participants

Short title: A randomized, open-label Phase 1 study to assess the relative bioavailability of a new formulation of minzasolmin in healthy participants

Regulatory agency identifying numbers:

EudraCT Number:	Not applicable
EU CT Number:	2024-511301-31
EUDAMED Number:	Not applicable
IND Number:	Not applicable
IDE Number:	Not applicable
NCT Number:	Not applicable

Rationale:

A new tablet formulation has been developed for minzasolmin. The current study UP0152 is designed to evaluate the relative bioavailability of a new tablet formulation compared with the current clinical formulation (ie, granules in capsule) under fasting conditions. UP0152 will provide safety, tolerability, and pharmacokinetic (PK) information of minzasolmin in fed and fasting conditions after single oral doses of minzasolmin █ administered once per period in healthy study participants. In addition, the study is also designed to evaluate the potential effect of a high-fat meal on the PK of minzasolmin when administered as tablet formulation.

Objectives, endpoints, and estimands:

Table 1-1: Objectives and endpoints

Objectives	Endpoints
Primary	

 To estimate the relative bioavailability of a new minzasolmin tablet formulation versus reference ‘granules in capsule’ formulation in healthy participants and to evaluate the effect of food with the new tablet formulation on the PK of minzasolmin. 	Primary PK Endpoint(s) 
 AUC_{0-t}, AUC, and C_{max} in fasting (for both granules in capsule and tablet formulations) and fed (tablet formulation only) conditions for minzasolmin
Secondary	

 To evaluate the safety and tolerability of single-dose administration of minzasolmin in healthy participants using different formulations in fed condition (tablet formulation) and fasting condition (tablet and ‘granules in capsule’ formulations). 	Secondary Safety Endpoint(s) 
 Occurrence of TEAEs Occurrence of treatment-emergent SAEs Occurrence of TEAEs leading to withdrawal from study
Other	

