1.3 Schedule of Activities

Procedure	Screening		Treatment Period A, B and C ^a							SFU ^b /ETV
			In-Clinic Period							
	D -28 to -2	D -1	D1^c	D2-5	D6^c	D7-10	D11^c	D12-14	D15	D18 (±2 days)
Informed consent	X									
Verification of inclusion/exclusion criteria	X	X								
Verification of withdrawal criteria			X	X	X	X	X	X	X	
Demography (height, weight, BMI)	X									
Physical examination	X	X	X ^d	X ^d	X ^d	X ^d	X ^d	X ^d	X ^d	X
General medical/procedure history	X									
Blood pregnancy test (WOCBP only)	X	X								X
Laboratory assessments (hematology, clinical chemistry, urinalysis, and FSH and estradiol) ^e	X	X		X (D5)		X (D10)			X	X
SARS-CoV-2 testing (PCR)		X								

Procedure	Screening		Treatment Period A, B and C ^a							SFU ^b /ETV
			In-Clinic Period							
	D -28 to -2	D -1	D1^c	D2-5	D6^c	D7-10	D11^c	D12-14	D15	D18 (±2 days)
Viral serology (HBsAg, HCV-Ab, HIV, and HBcAb)	X									
Urine cotinine, drug screen and urine alcohol test	X	X								
12-lead ECG ^f	X	X			X		X		X	X
Vital signs ^g	X	X	X		X		X		X	X
Randomization		X								
Minzasolmin administration			X		X			X		
Adverse event review	X	X	X	X	X	X	X	X	X	X
Prior- and concomitant medication review	X	X	X	X	X	X	X	X	X	X
Blood sampling for PK ^h			X	X	X	X	X	X	X	
Blood sampling for exploratory genetic biomarkers (DNA)		X								
Meals ⁱ		X	X	X	X	X	X	X		
Confinement	X		X	X	X	X	X	X		

Procedure	Screening		Treatment Period A, B and C ^a							SFU ^b /ETV
			In-Clinic Period							
	D -28 to -2	D -1	D1^c	D2-5	D6^c	D7-10	D11^c	D12-14	D15	D18 (±2 days)
Discharge									X	

BMI=body mass index; D=day; DBP=diastolic blood pressure; DNA=deoxyribonucleic acid; ECG=electrocardiogram; ETV=Early Termination Visit; FSH=follicle stimulating hormone; HBcAb=hepatitis B core antibody; HBsAg=hepatitis B surface antigen; HCV-Ab=hepatitis C virus antibody; HIV=human immunodeficiency virus; PCR=polymerase chain reaction; PK=pharmacokinetic(s); PR=pulse rate; SARS-CoV-2=severe acute respiratory syndrome coronavirus 2; SBP=systolic blood pressure; SFU=Safety Follow-Up; WOCBP=women of childbearing potential

^a Each participant will attend 3 Treatment Periods. Participants will be in the clinical center for the whole Treatment Period A, B and C.

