^b Study participants will have SFU procedures performed within 5 to 9 days after final dose. Participants who prematurely withdraw from the study will return to the clinic center for the ETV as soon as possible after the time of withdrawal and will have all SFU procedures performed.

^c Clinical assessments performed on Days 1, 6, and 11 need to be performed predose.

^d Complete physical examinations will be performed during Screening, at Day -1, and at SFU/ETV. Symptom-directed physical examinations will be performed during Treatment Periods.

^e Blood hematology and chemistry laboratory tests will be obtained in the fasting state following an overnight fast of at least 10 hours. Hepatic function tests only will also be performed 24 hours before each dosing (ie, Day 5 and Day 10). Note that FSH and estradiol will only be determined for females at the Screening Visit.

^f 12-lead ECG will be performed in single after a rest in supine position for at least 10 minutes before recordings, but can be repeated in triplicate if clinically indicated.

^g SBP, DBP, respiration rate, PR, and body temperature. Vital signs will be performed after a rest of at least 5 minutes.

^h The PK sampling timepoints will be: predose and at 0.5, 1, 1.5, 2, 4, 8, 12, 24, 36, 48, 72, and 96h after minzasolmin administration on Day 1, Day 6, and Day 11.

ⁱ Study participants will receive standard meals and snacks at appropriate times indicated by the clinic center, except when they are required to fast. All participants fast overnight for at least 10 hours before minzasolmin administration. Participants in Treatment A and B continue fasting for at least 4 hours after minzasolmin administration. Thereafter they receive a standard lunch. Fed study participants (Treatment C) should start the recommended high-fat high-calorie meal 30 minutes before administration of minzasolmin. Study participants should eat this meal in 30 minutes or less; however, minzasolmin should be administered 30 minutes after start of the meal. No food should be allowed for at least 4 hours postdose. During the rest of the day, study participants receive standard meals and snacks at appropriate times indicated by the clinic center.

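### The SAP's 4-day cut-off drops from the TEAE tables an AE that starts just before the Day 6 or Day 11 dose if no further dose is received, including when that AE causes the withdrawal

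*SAP*

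**What the plan says.** SAP 5.5.2 opens the TEAE window at the first treatment and closes it 4 days after the last treatment, inclusive. Beyond that, "AEs with a start date after 4 days of last treatment are defined as post-treatment", and "These events will not be included in any tabulated summaries but will be listed".

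Table 10 in the same section assigns AEs to periods by a different boundary. Period 1 ends "Prior to administration of treatment in Treatment Period 2", and Period 2 ends in the same way at the Period 3 dose. The Period 3 row has a beginning, "Start date is on or after administration of treatment in Treatment Period 3", and no end.

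The third secondary safety endpoint (Protocol 1.1, Table 1-1) is "Occurrence of TEAEs leading to withdrawal from study". The SAP serves it with a table by formulation and feeding condition, "Incidence of TEAEs leading to study discontinuation", and adds a companion table for permanent treatment discontinuation.

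On both Day 6 and Day 11 the Schedule of Activities (Protocol 1.3) marks "Verification of withdrawal criteria", a 12-lead ECG, vital signs and AE review. Its footnote c adds: "Clinical assessments performed on Days 1, 6, and 11 need to be performed predose".

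**The concern.** The 4-day limit is one day shorter than the interval between doses. The gap is invisible for a participant who goes on to the next dose, because that dose moves the last treatment forward. It opens for a participant who receives no further dose. The same AE, with the same onset after the same treatment, is then tabulated in one case and only listed in the other.

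The case is foreseeable. The predose checks on Days 6 and 11 are where the protocol looks for reasons not to continue, and they carry the only scheduled ECGs and vital signs after the first dose and up to the final dose. Clinically significant findings there are recorded as AEs (Protocol 7.1.2 and 8.3.2), and Protocol 7.1.2 and 7.2 provide for withdrawal. An AE found at such a check that ends participation belongs in the third secondary endpoint, yet the rule as written leaves it out. The error runs one way: it can remove such events and cannot add any.

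**Working it through.** **Inputs.** Doses on Days 1, 6 and 11 (SAP Table 4). Relative day = current date − dose date + 1 (SAP 5.1.1.1.2). TEAE if onset is no more than 4 days after the last treatment (SAP 5.5.2). Last treatment is read as the last one received, because the SAP does not define it separately.

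**Reproducing the plan's own days.**
- Washout 1: 2 − 1 + 1 = 2 to 5 − 1 + 1 = 5.
- Washout 3: 12 − 11 + 1 = 2 to 15 − 11 + 1 = 5.
- Safety follow-up: 16 − 11 + 1 = 6 to 20 − 11 + 1 = 10.

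These match Table 4 (relative days 2 to 5 and 6 to 10), so the arithmetic below uses the SAP's own day count.

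**Classifying a predose AE by calendar date.**

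| Onset | Next dose | Last treatment | Days after last treatment | Class |
|---|---|---|---|---|
| Day 6 predose | given | Day 6 or later | 0 or less | TEAE, Period 1 |
| Day 6 predose | not given, none later | Day 1 | 6 − 1 = 5 | post-treatment |
| Day 11 predose | given | Day 11 | 0 | TEAE, Period 2 |
| Day 11 predose | not given | Day 6 | 11 − 6 = 5 | post-treatment |

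**Classifying it by date and time.** Assume dosing at 08:00 and onset at 07:00. Elapsed time is 5 × 24 − 1 = 119 h, or 4.96 days, which exceeds 96 h, so the result is the same. Only counting completed 24-hour blocks (119 h gives 4) would keep the event a TEAE, and the SAP states no such rule.

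**How much time is affected.** From the first dose to the third is 2 × 120 = 240 h.
- Calendar days: only the hours from midnight to dosing on Days 6 and 11. With the assumed 08:00 dose this is 2 × 8 = 16 h, and 16/240 = 6.7%. Days 2-5 and 7-10 are inside the window.
- 96 h: the last 120 − 96 = 24 h before each scheduled dose, so 2 × 24 = 48 h, and 48/240 = 20%. An onset at 12:00 on Day 5 is then 100 h (4.17 days) after the Day 1 dose and falls outside if dosing stops. The hepatic tests 24 h before dosing sit exactly on the limit.

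**Effect per event.** The AE counts 1 in the TEAE tables if dosing continues. If it causes withdrawal, it counts 0 there and 0 in the discontinuation tables. With at most 18 participants per treatment, one event is 1/18 = 5.6% of a column.

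**The case against.** **Nothing is lost from the report.** This largely stands. The AE is listed with action taken and outcome. The withdrawal is counted in the table of discontinuations due to AEs (SAP 5.2) and in registry table DS_T_04 (SAP 6.5), and hypersensitivity and potential Hy's Law have their own listings (SAP 6.1.7). But SAP 5.2 tabulates by sequence, and every sequence contains all three treatments, so it does not replace the by-treatment endpoint table.

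**Four days is pharmacologically reasonable.** This stands. Five half-lives of the slowest analyte are 5 × 16 = 80 h, below 96 h (Protocol 4.2). The length is not the defect. The defect is that Periods 1 and 2 get up to 5 days or only 4, depending on later dosing.

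**The QTc route is not clean.** This stands in part. Protocol 7.1.2 names Day 6 and Day 11 among the Baseline time points for the change criterion, so its use at those ECGs is unclear. The absolute limits, vital signs and clinical-condition routes remain.

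A reader might also infer four stronger points that the documents do not support:
- *That classification turns directly on withdrawal due to the AE.* It turns on whether a further dose is received. A participant who leaves predose for an unrelated reason is treated in the same way.
- *That the open-ended Period 3 in Table 10 is an error.* Table 10 assigns a treatment and does not define TEAE. SAP 5.5.2 lists all AEs by formulation and feeding condition, so an AE on Days 16-20 needs that assignment.
- *That follow-up AEs on Days 16-20 must be tabulated.* The secondary endpoints and the registry commitment (Protocol 10.1.7) are limited to treatment-emergent events.
- *That the SAP hides a change by declaring none in 6.4.* The protocol sets no end to the TEAE window and leaves technical detail to the SAP (Protocol 9).

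**Conclusion.** The point holds, and it is minor. As written, SAP 5.5.2 treats an AE with onset in the predose hours of Day 6 or Day 11 as a TEAE of the preceding treatment if the next dose is given, and as an untabulated post-treatment event if no further dose is received. When that AE is the reason for stopping, the third secondary endpoint and the table for permanent treatment discontinuation miss it, and the error can only lower those counts.

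The conclusion rests on two readings: that last treatment means last received, and that the AE's onset is dated to the predose hours. It holds whether 4 days is counted in calendar days or as 96 h; the second reading widens the affected span to roughly the last 24 h before each scheduled dose. The documents give no rate of such events and assume minimal dropout among 18 participants, so the expected number cannot be stated and may well be zero. No PK result is touched.

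**What to change.** In SAP 5.5.2, define the TEAE window for Periods 1 and 2 as running from that period's dose through the predose assessments of the next scheduled dosing day (Day 6 or Day 11), whether or not that dose is given, and assign the AE to the preceding treatment. Keep 4 days after the Period 3 dose, and state whether this is calendar days or 96 h. Leave the Period 3 row of Table 10 open-ended, with a note that the table assigns AEs to a treatment and does not define treatment emergence.

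The cost is a few lines of SAP text and one condition in the TEAE flag. The downside is that Periods 1 and 2 keep a window up to 1 day longer than Period 3, as Table 10 already gives them when the next dose is taken. The design balances this across treatments: Period 3 is A in sequences 2 and 6, B in 3 and 4, and C in 1 and 5, so each treatment comes last in 2 of the 6 sequences.
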